#### 7.5.5.2. For subjects on TAF:

- If the eGFRCKD-EPI is confirmed to be  $\geq 15$  mL/min/1.73 m^2, no dose modifications are required

7.5.5.3. For subjects on TAF or TDF:

- All subjects with a confirmed  $eGFR_{CKD-EPI} < 15 \text{ mL/min/1.73 m}^2$  will be required to permanently discontinue treatment
- All subjects with a change from baseline serum creatinine of  $\geq 0.4 \text{ mg/dL}$  must have serum creatinine repeated, with a concurrent urinalysis and urine chemistry, within two weeks of receipt of results

#### **7.5.6. On-Treatment ALT Flare and Post-Treatment Exacerbation of Hepatitis Management**

On-Treatment ALT Flare is defined as:

- Confirmed (within 3 days of receipt of initial laboratory results) serum ALT  $> 2 \times$  baseline value and  $> 10 \times$  ULN, with or without associated symptoms

7.5.6.1. Management of ALT Flare in Subjects Receiving Study Medication

If laboratory results indicate elevation of ALT  $> 2 \times$  baseline and  $> 10 \times$  ULN, the following is recommended:

- Schedule the subject to return to the clinic as soon as possible (ideally within 3 days after initial laboratory results were drawn). During the visit, a clinical assessment of the subject will be performed. The assessment should include a physical examination and evaluation of the subject's mental status.
- Check the following laboratory parameters: serum ALT and AST, total bilirubin, INR, and serum albumin.
- If the ALT elevation is confirmed, the central clinical laboratory will conduct reflex testing for plasma HBV DNA, serology for HBV (HBsAg and HBsAb), HDV, HAV IgM, HCV, and HEV.

Based on the results of the confirmatory tests, the following treatment modifications are recommended:

#### **Elevated Liver Enzymes, Normal or Stable relative to baseline Liver Function Tests**

If ALT levels are elevated (i.e.,  $> 2 \times$  baseline and  $> 10 \times$  ULN) with normal or stable total bilirubin and INR relative to baseline, the subject may remain on study medication and should be monitored weekly as long as ALT levels return to normal or baseline level.

During monitoring, if the ALT values remain persistently elevated, the investigator should discuss with the Gilead Medical Monitor whether the study drug should be discontinued.

For subjects with bridging fibrosis or cirrhosis, study drug discontinuation with treatment-free follow-up is to be avoided due to the potential risk of exacerbation of hepatitis in the setting of low hepatic reserve which could lead to decompensation. Subjects with bridging fibrosis or cirrhosis should be placed on commercially available HBV therapy following study drug discontinuation.

### **Elevated Liver Enzymes, Elevated Liver Function Tests**

If ALT values are elevated (i.e.,  $> 2 \times$  baseline and  $> 10 \times$  ULN), and total bilirubin is confirmed to be  $2 \times$  baseline value, and INR is 0.5 above baseline, provided both are  $> ULN$ , the investigator should consider discontinuing study medication (upon discussion with the Gilead Medical Monitor, unless the safety of the subject is of immediate concern).

The subject should be monitored weekly as long as ALT, total bilirubin, and INR values remain elevated or above baseline values.

During monitoring, if the ALT values and the liver function tests remain persistently elevated, the investigator should discuss with the Gilead Medical Monitor whether the study drug should be discontinued.

For subjects with bridging fibrosis or cirrhosis, study drug discontinuation with treatment-free follow-up is to be avoided due to the potential risk of exacerbation of hepatitis in the setting of low hepatic reserve which could lead to decompensation. Subjects with bridging fibrosis or cirrhosis should be placed on commercially available HBV therapy following study drug discontinuation.

#### **7.5.6.2. Management of Exacerbation of Hepatitis in Subjects Who Have Discontinued Study Medication**

If laboratory results indicate (1) an ALT elevation  $> 2 \times$  baseline and  $> 10 \times$  ULN alone OR associated with (2) abnormal laboratory parameters suggestive of worsening hepatic function (total bilirubin  $2 \times$  baseline, INR 0.5 above baseline, provided both are  $> ULN$ ) and the subject is on no post-study therapy for HBV, the following is recommended:

- Schedule the subject to return to the clinic as soon as possible (ideally no later than 3 days after the initial laboratory values were drawn). During the visit, perform a clinical assessment of the subject.
- Check the following laboratory parameters: serum ALT and AST, total bilirubin, INR, and albumin.
- If the ALT elevation is confirmed, the central clinical laboratory will conduct reflex testing for plasma HBV DNA, serology for HBV (HBsAg and HBsAb), HDV, HAV IgM, HCV and HEV. If Plasma HBV DNA is increasing, the investigator should consider immediate initiation of approved therapy.
- The subject should be followed until laboratory parameters (ALT, total bilirubin, INR) return to normal or baseline up to a maximum of 6 months after the initial occurrence of the event.

### **7.6. Special Situations Reports**

#### **7.6.1. Definitions of Special Situations**

Special situation reports include all reports of medication error, abuse, misuse, overdose, reports of adverse events associated with product complaints, and pregnancy reports regardless of an associated AE, , and AE in an infant following exposure from breastfeeding.

Medication error is any unintentional error in the prescribing, dispensing, or administration of a medicinal product while in the control of the health care provider, subject, or consumer.

Abuse is defined as persistent or sporadic intentional excessive use of a medicinal product by a subject.

Misuse is defined as any intentional and inappropriate use of a medicinal product that is not in accordance with the protocol instructions or the local prescribing information.

An overdose is defined as an accidental or intentional administration of a quantity of a medicinal product given per administration or cumulatively which is above the maximum recommended dose as per protocol or in the product labelling (as it applies to the daily dose of the subject in question). In cases of a discrepancy in drug accountability, overdose will be established only when it is clear that the subject has taken the excess dose(s). Overdose cannot be established when the subject cannot account for the discrepancy except in cases in which the investigator has reason to suspect that the subject has taken the additional dose(s).

Product complaint is defined as complaints arising from potential deviations in the manufacture, packaging, or distribution of the medicinal product.

Occupational exposure is defined as exposure to a medicinal product as a result of one's professional or non-professional occupation.

## **7.6.2. Instructions for Reporting Special Situations**

### **7.6.2.1. Instructions for Reporting Pregnancies**

The investigator should report pregnancies in female study subjects that are identified after initiation of study medication and throughout the duration of the study, including the protocol – required post treatment follow-up period, to the Gilead PVE using the pregnancy report form within 24 hours of becoming aware of the pregnancy.

Refer to Section 7.3 and the CRF/eCRF completion guidelines for full instructions on the mechanism of pregnancy reporting.

The pregnancy itself is not considered an AE nor is an induced elective abortion to terminate a pregnancy without medical reasons.

Any premature termination of pregnancy (eg, a spontaneous abortion, an induced therapeutic abortion due to complications or other medical reasons) must be reported within 24 hours as an SAE. The underlying medical reason for this procedure should be recorded as the AE term.

A spontaneous abortion is always considered to be an SAE and will be reported as described in Sections 7.1.1 and 7.1.2. Furthermore, any SAE occurring as an adverse pregnancy outcome post study must be reported to Gilead PVE. The subject should receive appropriate monitoring and care until the conclusion of the pregnancy. The outcome should be reported to Gilead PVE using the pregnancy outcome report form. If the end of the pregnancy occurs after the study has been completed, the outcome should be reported directly to Gilead PVE. Gilead PVE contact information is as follows: Email: PPD and Fax: PPD

Pregnancies of female partners of male study subjects exposed to Gilead or other study drugs must also be reported and relevant information should be submitted to Gilead PVE using the pregnancy and pregnancy outcome forms within 24 hours throughout the duration of the study, including the protocol–required post treatment follow-up period. Monitoring of the subject should continue until the conclusion of the pregnancy. If the end of the pregnancy occurs after the study has been completed, the outcome should be reported directly to Gilead PVE, fax number PPD or email PPD Refer to Appendix 6 for Pregnancy Precautions, Definition for Female of Childbearing Potential, and Contraceptive Requirements.

### 7.6.2.2. Reporting Other Special Situations

All special situations reports (SSRs) will be recorded in the eCRF database within the timelines outlined in the eCRF completion guideline.

#### Electronic Special Situations Report (eSSR) Reporting Process

- Site personnel record all SSR data in the eCRF database and from there transmit the SSR information to Gilead PVE within 24 hours of the investigator's knowledge of the event throughout the duration of the study, including the protocol-required post treatment follow-up period. Detailed instructions can be found in the eCRF completion guidelines.
- If for any reason it is not possible to record the SSR information electronically, i.e., the eCRF database is not functioning, record the SSR on the paper serious adverse event reporting form and submit within 24 hours to:

**Gilead PVE:** Email: PPD [REDACTED]  
Fax: PPD [REDACTED]

**Gilead Medical Monitor:** Name: PPD [REDACTED]  
Phone: PPD [REDACTED]  
Fax: PPD [REDACTED]  
Email: PPD [REDACTED]

- As soon as it is possible to do so, any SSR reported via paper must be transcribed into the eCRF Database according to instructions in the eCRF completion guidelines.
- If an SSR has been reported via a paper form because the eCRF database has been locked, no further action is necessary.
- These reports must consist of situations that involve study IMP and/or Gilead concomitant medications, but do not apply to non-Gilead concomitant medications.
- Special situations involving non-Gilead concomitant medications does not need to be reported on the special situations report form; however, for special situations that result in AEs due to a non-Gilead concomitant medication, the AE should be reported on the AE form.
- Any inappropriate use of concomitant medications prohibited by this protocol should not be reported as "misuse," but may be more appropriately documented as a protocol deviation.

Refer to Section 7.3 and the CRF/eCRF completion guidelines for full instructions on the mechanism of special situations reporting.

All clinical sequelae in relation to these special situation reports will be reported as AEs or SAEs at the same time using the AE CRF/eCRF and/or the SAE report form. Details of the symptoms and signs, clinical management, and outcome will be reported, when available.

## 8. STATISTICAL CONSIDERATIONS

### 8.1. Analysis Objectives and Endpoints

#### 8.1.1. Analysis Objectives

The primary objectives of this study are:

- To evaluate the safety and tolerability of TAF 25 mg QD versus TDF-containing regimens as determined by the change from baseline in eGFRCKD-EPI at Week 24
- To evaluate the efficacy of TAF 25 mg QD versus TDF-containing regimens in maintaining viral suppression at Week 24

The secondary objectives of this study are:

- To evaluate the safety of TAF 25 mg QD versus TDF-containing regimens as determined by the percent change from baseline in hip and spine bone mineral density (BMD) at Weeks 24 and 48
- To evaluate the safety of TAF 25 mg QD versus TDF-containing regimens as determined by the change from baseline in serum creatinine at Weeks 24 and 48
- To evaluate the safety of TAF 25 mg QD versus TDF-containing regimens as determined by the change from baseline in eGFRCKD-EPI at Week 48
- To evaluate the efficacy of TAF 25 mg QD versus TDF-containing regimens in maintaining viral suppression at Week 48

The exploratory objectives of this study are:

- [REDACTED]
- [REDACTED]
- [REDACTED]
- [REDACTED]

### 8.1.2. Primary Endpoint

The **primary safety endpoint** is:

- Change from baseline in eGFRCKD-EPI of TAF 25 mg QD versus TDF-containing regimens at Week 24

The **primary efficacy endpoint** is:

- Proportion of subjects with HBV DNA < 20 IU/mL at Week 24

### 8.1.3. Secondary Endpoint

The **secondary safety endpoints** are:

- Percent change from baseline in hip and spine bone mineral density (BMD) of TAF 25 mg QD versus TDF-containing regimens at Weeks 24 and 48
- Change from baseline in serum creatinine of TAF 25 mg QD versus TDF-containing regimens at Weeks 24 and 48
- Change from baseline in serum eGFRCKD-EPI of TAF 25 mg QD versus TDF-containing regimens at Week 48

The **secondary efficacy endpoint** is:

- Proportion of subjects with HBV DNA < 20 IU/mL at Week 48

### 8.1.4. Other Endpoints of Interest

The **exploratory endpoints** are:

- [REDACTED]
- [REDACTED]
- [REDACTED]
- [REDACTED]
- [REDACTED]
- [REDACTED]
- [REDACTED]

█ [REDACTED]

█ [REDACTED]

## **8.2. Analysis Conventions**

### **8.2.1. Analysis Sets**

#### **8.2.1.1. Efficacy**

The primary analysis set for efficacy analysis is the Full Analysis Set (FAS), defined as all randomized subjects who receive at least one dose of study drug. Subjects will be analyzed according to the randomized treatment assignment.

#### **8.2.1.2. Safety**

The primary analysis set for safety analyses is the Safety Analysis Set (SAS), defined as all randomized subjects who receive at least one dose of study drug. Subjects will be analyzed according to the treatment actually received. All data collected during treatment will be included in the safety summaries. Data collected during TFFU will be summarized or listed separately.

#### **8.2.1.3. Pharmacokinetics**

The PK analysis set will include all subjects who are randomized and have received at least one dose of study medication and for whom concentration data of any analytes of interest (eg, TAF and TFV) are available. The PK analysis set will be used for analyses of concentration data.

CCI [REDACTED]

#### **8.2.1.4. Biomarkers**

The Biomarker analysis set will include all subjects who have evaluable biomarkers data.

## **8.3. Data Handling Conventions**

For the primary endpoint missing data will be handled using a missing = failure approach, unless otherwise specified.

For key secondary safety endpoints, an analysis will be performed using the Last Observation Carried Forward (LOCF) method to impute the missing data.

For other categorical secondary efficacy endpoints, missing data will be handled using a missing = failure approach. For the drug resistant mutations endpoint, a missing = excluded approach will be employed.

Sensitivity analyses will be performed as warranted.

#### **8.4. Demographic Data and Baseline Characteristics**

Demographic and baseline measurements will be summarized using standard descriptive methods by treatment group and overall.

Demographic summaries will include sex, race/ethnicity, and age.

Baseline data will include a summary of body weight, height, body mass index,  $\log_{10}$  HBV DNA level, years positive for HBV, ALT level ( $\leq$  ULN,  $>$  ULN), previous oral nucleoside/nucleotide treatment experience, previous interferon experience, and genotype.

#### **8.5. Efficacy Analysis**

##### **8.5.1. Primary Analysis**

The primary efficacy analysis will be conducted when the study subjects complete 24 weeks of the treatment period or discontinue prematurely. The response rate of each treatment arm will be presented. A two-sided 95% confidence interval, adjusted for the randomization stratification factor (the adjusted Mantel-Haenszel proportions), for the difference (TAF – TDF) in the proportion of subjects who maintained viral suppression (HBV DNA  $<$  20 IU/mL) at Weeks 24 and 48 will be constructed.

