- 6) Maintained on TDF alone or in combination with other approved antivirals for HBV prophylaxis or treatment
- 7) Have been on approved HBV OAV treatment for at least 12 weeks post-transplant prior to screening, with HBV DNA < LLOQ at screening

- 8) Screening  $eGFR_{CKD-EPI} < 90$  ml/min/1.73m^2
- 9) Male subjects and female subjects of childbearing potential who engage in heterosexual intercourse must agree to use protocol specified method(s) of contraception as described in [Appendix 6](#)
- 10) Women considered of child bearing potential (see [Appendix 6](#)) must have a negative serum pregnancy test at Screening and a negative urine test at Baseline before dosing
- 11) Must be willing and able to comply with all study requirements

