### 3.3. Study Treatments

Approximately 50 subjects with CHB and Stage 2 or greater chronic kidney disease and have received a liver transplant will be assigned to one of the two treatment arms (A: B) for 48 weeks. Randomization will be stratified by baseline renal function ( $eGFR_{CKD-EPI} < 50 \text{ ml/ min/1.73m}^2$  and  $\geq 50 \text{ ml/ min/1.73m}^2$ ).

- **Treatment Arm A:** approximately 25 subjects administered TAF 25 mg oral daily
- **Treatment Arm B:** approximately 25 subjects to continue administration of TDF alone or in combination with other approved antivirals per local practice

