## **5. INVESTIGATIONAL MEDICINAL PRODUCTS**

### **5.1. Randomization, and Treatment Codes**

The randomization will be performed via an Interactive Voice Response System (IVRS) or Interactive Web Response System (IWRS), whereby study treatment will be assigned to subjects according to the randomization schedule. A unique subject number will be provided during randomization. Eligible subjects (n = 50) will be randomized in a 1:1 ratio to receive either TAF or continue on TDF alone or in combination with other approved antivirals for 48 weeks. Randomization will be stratified by baseline renal function (eGFRCKD-EPI < 50 ml/min/1.73m^2 and ≥ 50 ml/min/1.73m^2).

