6.2.2. Analysis Methods for Secondary and Other Efficacy Endpoints

All the secondary and other efficacy endpoints involving proportions will be analyzed using the same statistical method (M = F) applied to the analysis of the primary efficacy endpoint. Sensitivity analyses will be performed using the M = E approach as well.

In addition, the proportion of subjects with HBV DNA < 20 IU/mL and the proportion of subjects with normal ALT (by central laboratory and AASLD criteria, M = F) will be separately plotted with 95% CI over time for FAS. Median (Q1, Q3) and mean (95% CI) of change from baseline in ALT (U/L) will also be plotted over time using observed data for FAS.

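### The protocol names no variance for its Mantel-Haenszel interval on the efficacy difference; with the usual one the interval is too short when few of about 50 suppressed subjects fail, and the final SAP omits the interval

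*Protocol*

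**What the plan says.** The primary efficacy endpoint is "Proportion of subjects with HBV DNA < 20 IU/mL at Week 24" (Protocol 8.1.2), and the secondary one is the same proportion at Week 48. For the difference, Protocol 8.5.1 specifies "A two-sided 95% confidence interval, adjusted for the randomization stratification factor (the adjusted Mantel-Haenszel proportions"), and 8.5.2 applies the same approach to the secondary endpoint. Neither section names a variance estimator or says what happens when a cell has no failures.

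Protocol 3.3 plans "approximately 25 subjects administered TAF 25 mg oral daily" and "approximately 25 subjects to continue administration of TDF alone or in combination with other approved antivirals per local practice". Protocol 5.1 adds: "Randomization will be stratified by baseline renal function", with two strata cut at an eGFR of 50. Inclusion criterion 7 requires subjects to enter "with HBV DNA < LLOQ at screening".

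Missing counts as failure in the primary analysis (Protocol 8.3, SAP 6.1.2). SAP 6.1.3 adds a missing = excluded sensitivity analysis. SAP 6.2.2 says that the by-arm proportions "will be separately plotted with 95% CI over time for FAS", again without a method.

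The final SAP describes no between-arm interval for these endpoints. SAP 3 says that results are descriptive, SAP 6.1.2 gives only the missing-data rule, and MH occurs only in the abbreviation list. SAP 6.3, which lists departures from the protocol's efficacy analyses, does not mention dropping the interval. SAP 2.1.2 refers to a separate Week 24 SAP, which is not among the documents.

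**The concern.** Everyone starts suppressed and the endpoint is staying suppressed, so response rates close to 100% are the natural expectation. The usual variance of a Mantel-Haenszel risk difference adds up p(1-p)/n over arms and strata, and a cell without failures adds nothing. The fewer the failures, the more of the sampling uncertainty disappears from the formula, down to an interval of zero width when nobody fails.

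The protocol plans no other between-arm inference on efficacy, and there was no sample size calculation. This interval is therefore the reader's only statement of how much about 50 subjects can show. If it is too short, it claims more precision than the trial has.

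**Working it through.** **Inputs.** 25 per arm (Protocol 3.3) and two strata (Protocol 5.1). The documents give no stratum split, so 13 and 12 per arm is assumed, with 20/5 and 22/3 as checks. They give no expected response rate, so a range is used. They state no interval or power, so there is no plan figure to reproduce.

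**Mantel-Haenszel, unadjusted variance.** With w_h = n1h·n2h/(n1h+n2h), the weights are 6.5 and 6, with sum 12.5.
- d = Σw_h(p1h - p2h)/Σw_h
- Var(d) = Σw_h²[p1h(1-p1h)/n1h + p2h(1-p2h)/n2h]/(Σw_h)²

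*All 50 respond.* Every p(1-p) is 0, so the interval is 0 to 0. The n-1 divisor and Sato's variance give the same, for all three splits.

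*One TAF failure, in the stratum of 13.* d = 6.5 × (12/13 - 1)/12.5 = -0.040. Var = 6.5² × (12/13)(1/13)/13 ÷ 12.5² = 0.2308/156.25 = 0.001477, so SE = 0.0384. The interval is -4.0 ± 1.96 × 3.84, or **-11.5 to +3.5 points**. Sato's variance gives -11.7 to +3.7.

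**Comparators.** The Wilson lower limit for 25/25 is 25/(25 + 3.84) = 0.867. Newcombe's interval for 25/25 v 25/25 is therefore ±13.3 points. Unstratified Miettinen-Nurminen gives ±13.6.

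Stratified Miettinen-Nurminen does not collapse. With no failures and difference d, the restricted estimates are 1 and 1-d, so the limit solves d = k(1-d), where k = 3.8415 × [6.5²/13 × 26/25 + 6²/12 × 24/23]/12.5² = 3.8415 × 6.510/156.25 = 0.160. Then d = 0.160/1.160, or ±13.8 points.

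| Responders, TAF v TDF | MH, unadjusted | Newcombe | Miettinen-Nurminen (unstratified) |
|---|---|---|---|
| 25/25 v 25/25 | 0 to 0 | -13.3 to +13.3 | -13.6 to +13.6 |
| 24/25 v 25/25 | -11.5 to +3.5 | -19.5 to +9.7 | -19.8 to +9.8 |

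**An adjusted variance.** Put (x+0.5)/(n+1) in the variance with divisor n-1. The stratum of 13 adds 6.5² × 2 × (13.5/14)(0.5/14)/12 = 0.2425. The stratum of 12 adds 6² × 2 × (12.5/13)(0.5/13)/11 = 0.2421. The sum over 156.25 is 0.00310, so the half-width at 50/50 is 1.96 × 0.0557, or 10.9 points. The collapse therefore depends on which variance is used.

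**Chance that all 50 respond** (common rate p, p^50, missing counted as failure):

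| p | 95% | 96% | 98% | 99% | 99.5% |
|---|---|---|---|---|---|
| p^50 | 0.08 | 0.13 | 0.36 | 0.61 | 0.78 |

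It exceeds one half only if p is above 0.5^(1/50) = 98.6%. Two proxies come from the Phase 3 studies in Protocol 1.2.3, each assuming no virologic failure:
- Exposure of at least 24 weeks, 98.3% TAF and 97.0% TDF (Table 1-5): 0.983^25 × 0.970^25 = 0.651 × 0.467 = 0.30.
- No virologic data at Week 48 (Table 1-2): 0.965^25 × 0.957^25 = 0.14 in one study, and 0.954^25 × 0.969^25 = 0.14 in the other.

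Shortening does not need 50/50. At the 24-week proxy rates, the chance that at least one arm has no failures, and so adds no variance, is 1 - (1 - 0.651)(1 - 0.467) = 0.81.

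**Exact coverage of the unadjusted interval** (binomial enumeration):
- 25 per arm, single stratum: 71% at true rates of 96% v 99%.
- Strata 13/12: 72% at 95% v 99%, and 77% at 96% v 98%.
- Strata 13/12, equal rates of 95%, 98% or 99%: 97% or more.
- The 0.5-adjusted variance, strata 13/12: 99.9% at 95% v 99% and at 96% v 98%.

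**The case against.** The strongest reply is that the collapse rests on a formula the protocol never states. A reader might infer that any Mantel-Haenszel interval shrinks to zero here. That does not follow, since an adjusted variance gives ±10.9 points. There is also a hint that the sponsor uses one. For the HBeAg-negative Phase 3 study, Table 1-2 reports -3.6 to 7.2, a half-width of 5.4. The unstratified plug-in value for 268/285 v 130/140 is 1.96 × √(0.0560/285 + 0.0663/140) = 5.1. In simulated allocations to that study's six strata, plug-in and n-1 forms reached at most about 5.2. This is inference only, because the stratum counts are not given and the published limits are rounded. It stands as a reason not to assume the plain form, but it does not put a variance into this trial's plan.

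A reader might also infer that zero width is the likely result. The documents do not support that. They give no expected rate, and under missing = failure one missed Week 24 sample rules out 50/50. The missing = excluded analysis is more exposed.

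Coverage is adequate when the two true rates are equal. The shortfall appears when they differ slightly.

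The study is exploratory, with no margin and no test, and each arm's rate is reported beside the difference. No formal decision turns on the interval. This also stands, and it limits the severity.

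Finally, the Week 24 and Week 48 analyses have been run, and the Week 24 SAP may name a method. That cannot be checked. However, SAP 6.1 and 6.2 say that these analyses will be repeated in the final analysis, so the method still needs stating there.

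**Conclusion.** The point holds as an unspecified method with a real consequence, and is moderate. Under the usual unadjusted variance, at about 25 per arm, the interval is too short when failures are few: -11.5 to +3.5 against -19.5 to +9.7 points with one TAF failure. Its coverage is about 71% to 77% at the small true differences tried. It has zero width if all 50 respond. The chance of that is 8% to 78% over assumed rates of 95% to 99.5%, and 14% to 30% on the Phase 3 proxies under missing = failure.

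These results rest on 25 per arm, the assumed stratum splits and response rates, and a variance that the protocol leaves open. A reader might go further and conclude that the efficacy finding would be invalid, or that equivalence would be declared wrongly. With no margin or test, the documents do not support that. The damage is to the precision reported.

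Separately, the protocol's between-arm interval is missing from the final SAP, and its absence is not explained.

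**What to change.** In the final SAP, for Weeks 24 and 48 and under both missing = failure and missing = excluded:
- Name one stratified score-type interval for TAF minus TDF, either stratified Miettinen-Nurminen or stratified Newcombe. Use it whatever the failure counts. Do not switch to an unstratified interval when a stratum has no failures: that picks the method from the outcome data, and a stratified score method does not need it.
- State Wilson or Clopper-Pearson limits for the by-arm proportion plots in SAP 6.2.2. At 25/25 the lower limits are 86.7% and 86.3% (0.025^(1/25)), whereas a Wald interval would again have zero width.
- Reconcile the SAP with Protocol 8.5.1 by writing the between-arm interval into SAP 6.1.2 and 6.2.2. Record the choice of method in SAP 6.3, noting that it follows the Week 24 and Week 48 analyses.

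The cost is new SAP text, since the final SAP has no Mantel-Haenszel wording to amend, and some programming for analyses that are to be repeated anyway. The downside is a wider reported interval, about ±13 to 14 points at 25/25 v 25/25.
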